## **7.6 FURTHER ENDPOINTS**

### Time to event endpoints

Further time to event endpoints will generally be analysed in a Cox proportional hazards model similar to the primary analysis on RS. If the endpoint does not include any cause of death, a CIF plot with all-cause mortality as competing risk will be displayed; otherwise, a CIF plot with causes of death not included in the endpoint as competing risk will be displayed.

If there are less than 14 patients with events, then only descriptive statistics will be presented.

Further time to event endpoints are the following:

- Time from first to second adjudicated HHF
- Time to first all-cause hospitalisation
- Time to new onset of atrial fibrillation
- Time to adjudicated MI (fatal or non-fatal)
- Time to adjudicated stroke (fatal or non-fatal)
- Time to adjudicated TIA
- Time to first event of all-cause mortality or all cause hospitalisation
- Time to first event of adjudicated CV death or adjudicated non-fatal MI
- Time to first event of adjudicated CV death or adjudicated non-fatal stroke
- Time to first event of adjudicated CV death, adjudicated non-fatal MI or adjudicated non-fatal stroke (3-point MACE)
- Time to progression to macro albuminuria (defined as UACR >300 mg/g) from baseline for patients with baseline UACR ≤ 300 mg/g

- Time to first new onset of sustained normo- or micro albuminuria (UACR  $\leq$  300 mg/g) in patients with macro albuminuria at baseline
- Time to first new onset of sustained normo albuminuria (UACR  $<$  30 mg/g) in patients with micro- or macro albuminuria at baseline
- Time to first event of composite renal endpoint or adjudicated CV death
- Time to first event of composite renal endpoint, adjudicated CV death or adjudicated HHF
- Time to first event of composite renal endpoint or all-cause mortality
- Time to achievement of NT-proBNP  $<$  1000 pg/mL
- Time to first acute kidney injury (based on the preferred term)
- Time to non-cardiovascular (non-CV) death (death cases not included in the definition of adjudicated CV death)
- Time to first investigator defined CV hospitalization

Composite renal endpoint defined as: *chronic dialysis or renal transplant or sustained\* reduction of  $\geq$ 40% eGFR (CKD-EPI)cr or*

- *(for patients with eGFR (CKD-EPI)cr  $\geq$ 30 mL/min/1.73 m^2 at baseline): sustained eGFR  $<$ 15 mL/min/1.73m^2*
- *(for patients with eGFR (CKD-EPI)cr  $<$ 30 mL/min/1.73 m^2 at baseline): sustained eGFR  $<$ 10 mL/min/1.73 m^2*

Chronic dialysis is regarded as chronic if the frequency of dialysis is twice or more per week for at least 90 days.

\*An eGFR (CDK-EPI)cr reduction is considered sustained, if it is determined by two or more consecutive post-baseline central laboratory measurements separated by at least 30 days (first to last of the consecutive eGFR values). If there is no additional measurement  $\geq$  30 days after the eGFR reduction is observed and the patient dies within 60 days of this measurement, then the eGFR reduction is also considered sustained

### Continuous endpoints:

The following endpoints will be evaluated by mixed models repeated measures (MMRM) as defined in the protocol.

- HbA1c change from baseline over time (OC-AD on the randomised set and OC-OT on the treated set)
- SBP, DBP change from baseline over time (OC-AD on the randomised set and OC-OT on the treated set)
- Weight change from baseline over time (OC-AD on the randomised set and OC-OT on the treated set)

- NT-pro BNP relative change from baseline over time (OC-AD on the randomised set and OC-OT on the treated set) (value will be transformed to the log scale before MMRM analysis. Estimates obtained from the model will then be back-transformed and reported on the original scale.)
- KCCQ overall summary score change from baseline at week 52 (OC-AD on the randomised set and OC-OT on the treated set) (model will include all timepoints up to week 52)
- KCCQ individual domains change from baseline at week 52 (OC-AD on the randomised set and OC-OT on the treated set) (model will include all timepoints up to week 52)
- KCCQ total symptom score change from baseline at week 52 (OC-AD on the randomised set and OC-OT on the treated set) (model will include all timepoints up to week 52)
- KCCQ based on patient-preferred outcome change from baseline at week 52 (OC-AD on the randomised set and OC-OT on the treated set) (model will include all timepoints up to week 52)
- UACR relative change from baseline over time (OC-AD on the randomised set and OC-OT on the treated set) (value will be transformed to the log scale before MMRM analysis. Estimates obtained from the model will then be back-transformed and reported on the original scale.)
- eGFR (CKD-EPI)cr change from baseline over time (OC-AD on the randomised set and OC-OT on the treated set)

As outlined in the protocol, the above endpoints will be analysed in a mixed model with repeated measures (MMRM), including age and eGFR (CKD-EPI)cr at baseline as linear covariates and visit by treatment interaction, baseline by visit interaction, geographical region, sex, baseline LVEF and status of diabetes at baseline as fixed effects. An additional factor of “week reachable” for the parameter in question, which for each patient is the theoretically reachable planned measurement based on the time of randomisation will adjust for the different planned study times.

An unstructured covariance structure will be used to model the within-patient errors.

Descriptive statistics will be calculated for the value at visit and change from baseline based on OC-AD on the randomised set and OC-OT on the treated set.

Additionally subgroup analyses will be performed as follows:

HbA1c change from baseline will be evaluated by status of diabetes (non-DM, pre-DM, DM).

NTproBNP change from baseline will be evaluated by baseline atrial fibrillation/atrial flutter (as determined by baseline ECG).

UACR will be evaluated by UACR at baseline (<30 mg/g, ≥30mg/g to ≤300mg/g, >300 mg/g).

In order to evaluate the mean effect on eGFR after approximately 3 years, the above described MMRM models will be used in the following way: a mean effect of the timepoints week 124, 148 and 172 will be calculated. Of the three timepoints, only those with at least 5 patients with a measurement at that timepoint will be included in the average calculation. This will be done for the imputations of OC-OT and OC-AD.

For MMRM subgroup analyses, the interaction term treatment-by-visit will be replaced by a treatment-by-subgroup-by-visit interaction term.

To support analysis of renal function, eGFR throughout the trial will be categorized according to the following CKD staging: All calculations for the staging of renal function will be based on the originally measured laboratory values, not on normalised values with BI standard reference ranges.

Table 7.6: 1 CKD staging

Stage	eGFR (mL/min/1.73m  )	Description	Label for displays	Additional labels#
1	≥90	Normal or high	≥90	≥90 (CKD 1)
2	60 to <90	Mildly decreased	60 to <90	60 to <90 (CKD 2)
3A	45 to <60	Mildly to moderately decreased	45 to <60	45 to <60 (CKD 3a)
3B	30 to <45	Moderately to severely decreased	30 to <45	30 to <45 (CKD 3b)
4	15 to <30	Severely decreased	15 to <30	15 to <30 (CKD 4)
5	<15	Kidney failure	<15	<15 (CKD 5)

A shift table from baseline to last value on treatment for eGFR (CKD-EPI)cr will be provided.

In cases where urine albumin values are reported to be below the quantification limits (e.g. <3 mg/L) the albumin / creatinine ratio is determined as missing and will not be replaced by estimated values.

Transitions from baseline to last value on-treatment based on the following UACR categories: normal (<30mg/g), microalbuminuria (30-≤300 mg/g and macroalbuminuria (>300 mg/g) will be presented.

For an evaluation of follow-up after discontinuation of trial medication an additional summary of the NT-proBNP, FG, eGFR, UACR, creatinine and the KCCQ endpoints as above will be produced. This summary will include descriptive statistics for baseline, actual values and change from baseline to last on-treatment value and follow-up, and change from last on-treatment assessment to follow-up. The TS-FU patient set will be the basis for this summary, but only those patients with a valid baseline, last value on treatment and follow-up value will be included in all displays. Analyses will be repeated for patients with at least 52 weeks of cumulative exposure (excluding treatment gaps). FG analysis will also be conducted by DM status at baseline (3 categories).

Analyses of change from baseline to LVOT and FU on the TS-FU outlined above will be additionally modelled, separately for LVOT and FU. An analysis of covariance (ANCOVA) model including treatment group, sex, geographical region, baseline LVEF and status of diabetes at baseline as fixed effects and baseline eGFR (CKD-EPI)cr (continuous), age (continuous), and baseline of the endpoint (if not already included) as linear covariates will be used.

In addition to the ANCOVA models described above, descriptive statistics will be presented also for creatinine for the value at visit and change from baseline based on OC-AD on the randomised set and OC-OT on the treated set.

In addition to the analyses defined above, KCCQ clinical summary score, clinical symptoms and physical limitations domain will be analysed in two responder analyses (1) defining an increase of 5 points or more from baseline as improvement and (2) defining a reduction of 5 points or more as deterioration.

The frequency and percentage (relative to RS) of patients with improvement as well as the frequency and percentage of patients with deterioration will be described. Patients lost to follow-up or who withdrew consent prior week 52 as well as patients who died prior week 52 will be considered as having a deterioration (no improvement) in KCCQ.

Improvement and deterioration will be analysed in separate logistic regression models including treatment, age (continuous), eGFR (CKD-EPI)cr at baseline (continuous), region, sex, baseline LVEF (categorical), status of diabetes at baseline, and baseline value of the KCCQ domain analyzed.

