5.1.3 Further endpoints

- Time from first to second adjudicated HHF
- Time to first all-cause hospitalisation
- Occurrence of adjudicated HHF within 30 days after first adjudicated HHF
- Occurrence of adjudicated HHF and CV death. This endpoint will account for clinical hierarchies in composite outcomes, i.e. CV death is ascribed greater importance than HHF (see win ratio in [Section 7.3.3](#))
- New onset of atrial fibrillation
- Adjudicated MI (fatal or non-fatal)
- Adjudicated stroke (fatal or non-fatal)
- Adjudicated TIA
- Composite of time to first event of all-cause mortality and all-cause hospitalisation
- Composite of adjudicated CV death or adjudicated non-fatal MI
- Composite of adjudicated CV death or adjudicated non-fatal stroke
- Adjudicated CV death, adjudicated non-fatal MI, adjudicated non-fatal stroke (3-point MACE)
- Progression to macro albuminuria (defined as UACR >300 mg/g) from baseline for patients with baseline UACR ≤ 300 mg/g
- Time to first new onset of sustained normo- or micro-albuminuria (UACR ≤ 300 mg/g) in patients with macro albuminuria at baseline
- Time to first new onset of sustained normo-albuminuria (UACR < 30 mg/g) in patients with micro- or macro-albuminuria at baseline
- eGFR (CKD-EPI)_{cr} change from baseline to 30 days after treatment stop
- Composite of sustained reduction of ≥40% eGFR (CKD-EPI)_{cr} or sustained eGFR(CKD-EPI)_{cr} <15 mL/min/1.73 m² (< 10 mL/min/1.73 m² for patients with eGFR (CKD-EPI)_{cr} <30 mL/min/1.73 m² at baseline) or adjudicated CV death
- Composite of sustained reduction of ≥40% eGFR (CKD-EPI)_{cr} or sustained eGFR(CKD-EPI)_{cr} <15 mL/min/1.73 m² (< 10 mL/min/1.73 m² for patients with eGFR (CKD-EPI)_{cr} <30 mL/min/1.73 m² at baseline) or all-cause mortality
- Composite of sustained reduction of ≥40% eGFR (CKD-EPI)_{cr} or sustained eGFR (CKD-EPI)_{cr} <15 mL/min/1.73 m² (< 10 mL/min/1.73 m² for patients with eGFR (CKD-EPI)_{cr} < 30mL/min/1.73 m² at baseline), adjudicated CV death, or adjudicated HHF
- Change from baseline in KCCQ overall summary score at week 52
- Change from baseline in KCCQ total symptom score at week 52
- Change from baseline in KCCQ individual domains at week 52

- Change from baseline in KCCQ based on patient-preferred outcome at week 52
- Change in NYHA class from baseline at week 52
- Change from baseline in Health-related quality of life measured by EQ-5D
- Health economic analysis by Health Care Resource Utilisation (HCRU)

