**6.7 BASELINE, TIME WINDOWS AND CALCULATED VISITS**

For serum creatinine and values based on upon this measurement such as eGFR, baseline will be defined as the mean of all available measurements from the screening visit until start of randomised trial medication. For all other endpoints, baseline will be defined as the last available measurement before start of randomised trial medication.

Since the protocol specifies, that all measurements are taken at visit 2 before any intake of trial medication, all measurements at the first day of drug intake are assumed to qualify as baseline assessments.

For randomised patients without any treatment intake: For serum creatinine and values based on upon this measurement such as eGFR, baseline will be defined as the mean of all available measurements from the screening visit until and including the day of randomisation. For all other endpoints, baseline will be defined as the last available measurement before or on the day of randomisation.

Measurements taken after the first intake of randomised trial medication will be considered on-treatment values if they have been obtained up to end of the parameter specific follow-up period as defined in [Table 6.7: 1](#) below and will be assigned to the randomised study drug for efficacy and safety analyses.

Measurements taken after the end of the endpoint specific follow-up period after the last intake of study drug will be considered post-treatment values.

On-treatment (for OC-OT analysis) or all post-randomisation (for OC-AD analysis) efficacy and safety measurements will be assigned to visits based on time windows around the planned visit dates. These time windows are defined based on the planned number of days after the date of first administration of study drug.

The time window for the first visit after randomisation starts on the day after the first intake of study drug. The midpoint between two on-treatment visits defines the end of a time window, with the midpoint being included in the time window of the preceding visit.

Table 6.7: 1 Time windows for post-baseline efficacy measurements scheduled for each on-treatment visit for the first 3 years

Visit number	Visit label	Planned days	Time window (actual days after baseline)	
			Start	End
Endpoints assessed at each on-site visit (e.g. creatinine / eGFR)				
2	Baseline A	1	NA	1
3	Week 4	29	2	57
4	Week 12	85	58	155
6	Week 32	225	156	295
8	Week 52	365	296	449
10	Week 76	533	450	617

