12	Week 100	701	618	785
14	Week 124	869	786	953
16	Week 148	1037	954	1121
18	...			
FU	FU	Trt stop + 30 days	Trt stop + 23 days	Trt stop + 45 days
KCCQ				
2	Baseline A	1	NA	1
4	Week 12	85	2	154
6	Week 32	225	155	295
8	Week 52	365	296	435
EOT	EOT / Post week 52	NA	436	Trt stop
FU	FU	Trt stop + 30 days	Trt stop + 23 days	Trt stop + 45 days

A Only values taken prior to the start of treatment with randomised study drug can be considered baseline values. Time windows will be used for assignment of measurements to scheduled visits.

For examinations that are not planned at every on-treatment visit, the time windows will be defined according to the same algorithm, based on the midpoint between the planned visit day of such an examination. Examples for eGFR and KCCQ can be found in Table 6.7: 1.

Only one observation per time window will be selected for analysis at an on-treatment visit – the non-missing value will be selected which is closest to the protocol planned visit day. If there are two observations which have the same difference in days to the planned day or if there are two observations on the same day, the first value will be used.

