#### Endpoints based on laboratory data only

Patients who already fulfil the respective condition at baseline are not considered in the number of patients at risk for this endpoint.

If a baseline laboratory measurement is not available for the parameter of interest, it is assumed that the patient did not experience the condition corresponding to the endpoint at baseline and the patient is included in the patients at risk for this endpoint. Patients without an event and available post-baseline laboratory measurements will be considered censored at the date of last laboratory sampling of the corresponding parameter. Patients with missing baseline laboratory required to derive a change from baseline and patients without laboratory data following the baseline measurement will be censored on the date of randomisation.

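### SAP 7.6 sets UACR to missing when urine albumin is below the quantification limit, although the category is nearly always known to be <30 mg/g; the missing-baseline default in SAP 6.8.3 also conflicts with the populations of two albuminuria-improvement endpoints (further endpoints only)

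*SAP*

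**What the plan says.** For albumin below the quantification limit (3 mg/L is given only as an example), SAP 7.6, under continuous endpoints, states that "the albumin / creatinine ratio is determined as missing and will not be replaced by estimated values". The next sentence plans a shift table whose lowest UACR category is normal, <30 mg/g. No section assigns below-limit results to that category.

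Three other rules then decide what is shown:
- **Baseline (SAP 6.7):** "For all other endpoints, baseline will be defined as the last available measurement before start of randomised trial medication".
- **Visit windows (SAP 6.7):** "the non-missing value will be selected which is closest to the protocol planned visit day".
- **Tabulations and subgroups:** SAP 7 uses all patients as denominator and shows a missing category when there are missing values. SAP 6.4 leaves missing subgroup categories out of the analysis.

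For endpoints based only on laboratory data, SAP 6.8.3 first says: "Patients who already fulfil the respective condition at baseline are not considered in the number of patients at risk for this endpoint". It then assumes that a patient without a baseline value "did not experience the condition corresponding to the endpoint at baseline and the patient is included in the patients at risk". A later sentence censors at randomisation where the missing baseline is needed to derive a change.

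SAP 7.6 defines the two improvement endpoints for narrower populations. Return to UACR of 300 mg/g or less is assessed "in patients with macro albuminuria at baseline", and return to below 30 mg/g "in patients with micro- or macro albuminuria at baseline". Protocol 5.1.3 agrees, for example "Time to first new onset of sustained normo-albuminuria (UACR < 30 mg/g) in patients with micro- or macro-albuminuria at baseline".

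**The concern.** Declining to invent a number for a continuous analysis is defensible. Discarding a category that needs no invented number is not. A below-limit result is the lowest the assay can report, yet under these rules it is the one result that cannot be shown as normal. It becomes missing, or a different and necessarily quantified sample stands in for it. A patient who improves to below the limit cannot have that sample counted toward, or used to confirm, normoalbuminuria.

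The second issue is a conflict of text. The missing-baseline default suits progression to macroalbuminuria, where not having the condition at baseline is the state required for entry. For the two improvement endpoints the condition is a low UACR, so the default runs backwards: a patient whose baseline samples were all below the limit is presumed albuminuric and enters the risk set. Two programmers could build different risk sets from the same SAP.

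**Working it through.** The plan gives no figure to reproduce here, so the check is a bound, a trace of the rules and a simulation on assumed inputs.

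**1. The bound.** UACR (mg/g) = albumin (mg/L) / urine creatinine (g/L). If albumin is below limit L, then UACR < L / creatinine. The creatinine that guarantees UACR <30 is L/30:
- L = 2 mg/L: 0.067 g/L
- L = 3 mg/L: 0.10 g/L
- L = 5 mg/L: 0.167 g/L
- L = 10 mg/L: 0.333 g/L

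For UACR of 300 mg/g or less at L = 3 mg/L, 0.01 g/L is enough. Very dilute urine is the only exception.

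**2. Assumed inputs.** The documents give no UACR or urine creatinine distribution. Assumed: log-normal UACR with geometric mean (GM) 15, 22 or 35 mg/g; total log-SD 1.5; within-patient log-SD 0.5, 0.7 or 1.0; urine creatinine median 0.7 g/L, log-SD 0.5, independent between visits; L = 3 mg/L. Samples at Visits 1 and 2 follow the protocol flow chart.

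**3. Samples below the limit.** Log albumin has mean ln(0.7 × GM) and SD √(1.5² + 0.5²) = 1.58. The share below the limit is Φ[(ln 3 − ln(0.7 × GM)) / 1.58]:
- GM 15: Φ(−0.79) = 21%
- GM 22: Φ(−1.03) = 15%
- GM 35: Φ(−1.33) = 9%

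Over 99.9% of these have a creatinine that proves UACR <30.

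**4. No baseline UACR.** Both pre-treatment samples must be below the limit. At within-SD 0.7 the correlation of log albumin between visits is (1.5² − 0.7²)/(1.5² + 0.5²) = 1.76/2.50 = 0.70, giving 12.4 / 7.9 / 4.2% for GM 15 / 22 / 35. Over all nine scenarios the range is 3-14%. With 2850 patients (Protocol 7.7) to about 3600 (SAP 9.6), that is 0.03 × 2850 ≈ 86 to 0.14 × 3600 ≈ 504 patients.

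**5. Baseline display.** At GM 22, within-SD 0.7, the true normal share is Φ(ln(30/22)/1.5) = Φ(0.21) = 58%, and the table would show 50%. Of that 8.3-point fall, 7.9 points are the missing row and about 0.5 points are patients shown as albuminuric through an earlier sample. Across scenarios, below-limit Visit 2 results still show as normal in 34-52%, as missing in 31-65%, and as albuminuric in 0.5-17% (0.1-2.0% of all patients). Of below-limit last on-treatment results, 60-78% still show as normal. The follow-up summaries in SAP 7.6, which need valid baseline, last on-treatment and follow-up values, lose 11-26% of patients.

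**6. Improvement endpoints, SAP 7.6 populations.** Taking sustained to mean two consecutive available values, 0.5-10% of sustained normalisations are lost and 1-10% are delayed. Hazard ratios under a common UACR ratio of 0.84 change by at most 0.02; at GM 22, within-SD 0.7, 1.29 becomes 1.28 for return to <30 and 1.19 stays 1.19 for return to ≤300 mg/g.

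**7. Contingent case: the SAP 6.8.3 default applied literally.** At within-SD 0.7 the share of the ≤300 mg/g risk set with no baseline UACR is that percentage divided by itself plus the macroalbuminuric percentage:
- GM 15: 12.4/(12.4 + 2.3) = 84%
- GM 22: 7.9/(7.9 + 4.1) = 66%
- GM 35: 4.2/(4.2 + 7.6) = 36%

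Over all scenarios this is 28-86%, and 5-30% for the <30 mg/g risk set. At GM 22 the hazard ratios move from 1.29 to 1.18 and from 1.19 to 1.02.

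**8. Log-UACR model.** Deleting below-limit values shifts the estimated ratio by +0.01 to +0.04 (toward 1) for a common ratio of 0.84, and by −0.018 to +0.001 (mostly away from 1) if the effect is 0.75 in albuminuric patients and 1.0 in others. With no effect the shift stays within 0.006.

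**The case against.** **The large effects need an unnatural reading.** An endpoint's own population normally overrides a general default, and both documents name the population. This stands. A reader might infer from step 7 that the planned hazard ratios for albuminuria improvement are seriously distorted, or that the macroalbuminuria analysis consists mainly of patients with normal UACR. The documents do not support that; it follows only if SAP 6.8.3 overrides the endpoint definitions.

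**Censoring at randomisation may settle it.** SAP 6.8.3 censors patients whose missing baseline is needed to derive a change. If that covered these endpoints, such patients would contribute nothing. But a UACR threshold needs no derived change, so the sentence does not clearly apply.

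**The baseline effect is mostly visible.** This also stands. A reader might take the fall from 58% to 50% normal as hidden misclassification, but nearly all of it is a labelled missing row.

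**Everything numerical is assumed.** True. The limit is an example, and the SAP defines sustained only for eGFR, so step 6 rests on an assumed rule for UACR. The bound in step 1 does not depend on any of this.

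**Not substituting values is a deliberate choice.** It is, and it can stay for the primary continuous analyses. It does not answer why a category that is known should be discarded.

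**Conclusion.** The concern holds for the categorical and time-to-event UACR analyses. Following SAP 7.6 as written, results provably below 30 mg/g are shown as missing or under another sample's value, and they cannot support a return to normoalbuminuria. On the assumed inputs this touches 9-21% of samples and leaves 3-14% of patients without a baseline UACR, with 0.1-2.0% of patients shown as albuminuric at baseline.

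The conflict between SAP 6.8.3 and SAP 7.6 is real on the text but has a natural resolution: the SAP 7.6 populations govern, and hazard ratios then change by at most 0.02.

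The reach is limited. UACR appears only in the demographics column of Table 6.4:1, and the affected analyses are further or descriptive endpoints. The primary and key secondary analyses and the testing hierarchy are untouched. A material bias in the log-UACR treatment effect is not shown: the shift is small, can go either way, and nearly vanishes under no effect. This is a point to consider, not a flaw in the trial's main conclusions.

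**What to change.** 1. For categorical, shift, baseline-subgroup and time-to-event UACR analyses, classify a below-limit result as <30 mg/g when limit / urine creatinine is below 30, and use it as the baseline, visit, last or confirming value.
2. State that the populations in SAP 7.6, not the missing-baseline default in SAP 6.8.3, define the risk sets of the two improvement endpoints. Keep the default for progression to macroalbuminuria.
3. Keep the planned log-UACR MMRM and the follow-up summaries and ANCOVA. Add one sensitivity analysis of each with below-limit values handled numerically, by limit substitution or left-censoring. Item 1 alone does not restore the patients lost from the follow-up analyses, which need a number. In the model of UACR by baseline UACR, take the category and the baseline covariate from the same sample; otherwise a patient could be classed as <30 while the covariate is an earlier value of 30 or more.
4. Report below-limit counts by arm and visit.

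The cost is a few sentences of SAP wording and modest programming. Protocol 5.3.4.1 has UACR calculated at the central laboratory, so urine creatinine must be transferred if it is not already in the data.
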